6.5. Instructions for Initiation of a New Cycle

A new course of treatment may begin on the scheduled Day 1 of a new cycle if all of the following are met:

- ANC $> 1.0 \times 10^9/L$
- Platelet count $\geq 30 \times 10^9/L$
- Any other study drug-related adverse event must have resolved to grade 1 or baseline (see Appendix 2)
- Serum uric acid and creatinine concentrations must return to baseline prior to carfilzomib doses during Cycles 1 and 2

If these conditions are not met on Day 1 of a new cycle, the subject will be evaluated weekly, and a new treatment cycle will not be initiated until the toxicity has resolved, as described above.

If elotuzumab, carfilzomib or lenalidomide are held for the remainder of the previous cycle or the new cycle is delayed due to residual toxicity on the planned Day 1 of the next cycle, then the new cycle will be started at 1 dose decrement.

If a delay of starting a new cycle is greater than 21 days, the subject should be discontinued from treatment, unless continuing treatment is mutually agreed upon by the site Lead Principal Investigator at the University of Chicago and the Co-Investigator at the treating institution.

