Nominal Lenalidomide Dose	Dose -1	Dose -2	Dose -3
25 mg Days 1-21	15 mg	10 mg	5 mg

Table 6-3 Dexamethasone Dose Adjustments

Nominal Dexamethasone Dose	Dose -1	Dose -2	Dose -3
40mg or 20 mg	Reduce dexamethasone by 50% from starting dose; however, the 20-mg IV dose of dexamethasone given before the infusion on the day of elotuzumab infusions must not be decreased.	dexamethasone on the day when elotuzumab is	Discontinue dexamethasone

^{*}Split dosing of dexamethasone on days 1,2, 8,9, 15,16, 22,23 may be implemented to control toxicities that do not require a dose reduction. Split dosing requires the approval of the Lead Principal Investigator

6-4 Elotuzumab Dose Adjustments

No dose reductions for elotuzumab are allowed. If Elotuzumab is held on Day 1 of a new cycle, treatment with carfilzomib/lenalidomide/dexamethasone will also be delayed. If elotuzumab is held during any cycle on days 8, 15, or 22, the treating investigator will decide if lenalidomide, carfilzominb, and/or dexamethasone will be held using recommended guidance for retreatment below. Treatment may be delayed for a maximum of 21 days (see section 6.5.2.1 for details).

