6.6.1.1. Hematologic Toxicity

Table 6-5 Dose Modification Guidelines for Hematologic Toxicities

When Platelets:	Lenalidomide	Carfilzomib		Elotuzumab
Fall to < 30 x 10 ⁹ /L	 Hold dose, follow CBC weekly Hold prophylactic anticoagulation until platelets return to ≥ 30 × 10⁹/L Then resume at 1 dose decrement 	If platelets 10-30 x10 ⁹ /L without evidence of bleeding	Hold With resolution restart at previous dose	Hold Upon resolution elotuzumab can be restarted at the treating physician's discretion
		If evidence of bleeding or platelets < 10 x10 ⁹ /L	Hold With resolution restart at previous dose	Hold Upon resolution elotuzumab can be restarted at the treating physician's discretion
For each subsequent drop to < 30 x $10^9/L$	 Hold dose, follow CBC weekly Hold prophylactic anticoagulation until platelets return to ≥ 30 × 10⁹/L Then resume at additional dose decrement 	If platelets 10-30 x 10 ⁹ /L without evidence of bleeding	Hold With resolution restart at previous dose	Hold Upon resolution elotuzumab can be restarted at the treating physician's discretion
		If evidence of bleeding or platelets < 10 x10 ⁹ /L	Hold With resolution restart at 1 dose decrement	Hold Upon resolution elotuzumab can be restarted at the treating physician's discretion

Grade 4 thrombocytopenia without evidence of bleeding, carfilzomib dosing may occur at the discretion of the Treating Investigator. However, subjects should receive supportive measures in accordance with institutional guidelines.

Table 6-5 Dose Modification Guidelines for Hematologic Toxicities

When ANC:	Lenalidomide	Carfilzomib		Elotuzumab
Fall to < 0.75 x 10 ⁹ /L	 Hold dose, administer myeloid growth factor Follow CBC weekly Resume at full dose when ANC ≥ 0.75 x 10⁹/L 	If ANC 0.5-0.75 x 10 ⁹ /L	Continue at full dose	Continue at full dose
		If ANC $< 0.5 \times 10^9 / L$	• Hold • Resume at 1 dose decrement when ANC returns to ≥ 0.5 x10 ⁹ /L	Hold Upon resolution elotuzumab can be restarted at the treating physician's discretion
For each subsequent drop to < 0.75 x 10 ⁹ /L	 Hold dose, administer myeloid growth factor Follow CBC weekly Resume at 1 dose decrement when ANC ≥ 0.75 x 10⁹/L 	If ANC 0.5-0.75 x 10 ⁹ /L	Continue at full dose	Hold Upon resolution elotuzumab can be restarted at the treating physician's discretion
		If ANC $< 0.5 \times 10^9 / L$	• Hold • Resume at 1 dose decrement when ANC returns to ≥ 0.5 x10 ⁹ /L	Hold Upon resolution elotuzumab can be restarted at the treating physician's discretion

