6.6.1.2. Non-hematologic Toxicity

Table 6-6 Dose Modifications for Non-hematologic Toxicity

	Recommended Action					
Non-heme toxicity	Lenalidomide	Carfilzomib	Elotuzumab			
Non-Blistering Rash						
Grade 3	Hold lenalidomide dose; follow weekly If the toxicity resolves to ≤ Grade 1 prior to Day 21 of the current cycle, restart at 1 dose decrement and continue the cycle until Day 21 of the current cycle.	Hold (if Treating Investigator's opinion is possibly related to Carfilzomib) until ≤ Grade 1, reinstitute at current dose	Hold Upon resolution elotuzumab can be restarted at the treating physician's discretion			
Grade 4	Discontinue lenalidomide study drug.	Hold until \leq Grade 1, reinstitute at current dose.	Hold Upon resolution elotuzumab can be restarted at the treating physician's discretion			

Table 6-6 Dose Modifications for Non-hematologic Toxicity

Recommended Action					
Non-heme toxicity	Lenalidomide	Carfilzomib	Elotuzumab		
Desquamating (blistering) rash – any grade	Discontinue lenalidomide study drug.	Hold until ≤ Grade 1, reinstitute at current dose.	Hold Upon resolution elotuzumab can be restarted at the treating physician's discretion		
Erythema multiforme ≥ Grade 3	Discontinue lenalidomide study drug.	Hold until \leq Grade 1, reinstitute at current dose.	Hold Upon resolution elotuzumab can be restarted at the treating physician's discretion		
Sinus bradycardia/ other cardiac arrhythmia					
≤ Grade 2	Hold lenalidomide dose. Follow at least weekly. If the toxicity resolves to ≤ Grade 1 prior to Day 21, restart at 1 dose decrement and continue the cycle until Day 21.	Hold until ≤ Grade 1, reinstitute at current dose.	Hold Upon resolution elotuzumab can be restarted at the treating physician's discretion		
≥ Grade 3	Discontinue lenalidomide study drug	Hold until ≤ Grade 1, reinstitute at current dose.	Hold Upon resolution elotuzumab can be restarted at the treating physician's discretion		
Allergic reaction/hypersensitivity					
Grade 2 – 3	Hold lenalidomide dose. Follow at least weekly. If the toxicity resolves to ≤ Grade 1 prior to Day 21, restart at 1 dose decrement and continue the cycle until Day 21.	Hold until ≤ Grade 1, reinstitute at current dose.	Discontinue		
Grade 4	Discontinue	Discontinue	Discontinue		

Table 6-6 Dose Modifications for Non-hematologic Toxicity

	Recommended Action				
Non-heme toxicity	Lenalidomide	Carfilzomib	Elotuzumab		

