Tumor lysis syndrome (≥ 3 of the following: ≥ 50% increase in creatinine, uric acid, or phosphate;≥ 30% increase in potassium;≥ 20% decrease in calcium; or ≥ 2-fold increase in LDH	Hold lenalidomide until all abnormalities in serum chemistries have resolved. Reinstitute at full doses.	Hold carfilzomib until all abnormalities in serum chemistries have resolved. Reinstitute at full doses.	Hold Upon resolution elotuzumab can be restarted at the treating physician's discretion		
Infection Grade 3 or 4	Hold lenalidomide until systemic treatment for infection is completed. If no neutropenia, restart lenalidomide at full dose. If neutropenic, follow neutropenic instructions.	Hold carfilzomib until systemic treatment for infection is completed If no neutropenia, restart carfilzomib at full dose. If neutropenic, follow neutropenic instructions.	Hold Upon resolution elotuzumab can be restarted at the treating physician's discretion		
Herpes zoster or simplex of any grade	Hold lenalidomide until lesions are dry. Reinstitute at full doses.	Hold carfilzomib until lesions are dry. Reinstitute at full doses.	Hold When lesions are dry elotuzumab can be restarted at the treating physician's discretion		
Grade 2 neuropathy with pain or any Grade 3 neuropathy	Hold until ≤ Grade 2. Then restart lenalidomide at 1 dose decrement	Withhold until toxicity is resolved or returned to baseline After resolution, consider if restarting CFZ at the same dose or at a reduced dose is appropriate. If tolerated, the reduced dose may be escalated to the previous dose at the discretion of the physician	Hold Upon resolution elotuzumab can be restarted at the treating physician's discretion		
Grade 4 neuropathy	Discontinue	Discontinue	Hold Upon resolution elotuzumab can be restarted at the treating physician's discretion		
Renal dysfunction					
Serum creatinine > 2 mg/dL	Base dose reduction on calculated GFR (below)	Base dose reduction on calculated GFR (below)	Hold Upon resolution elotuzumab can be		

Table 6-6 Dose Modifications for Non-hematologic Toxicity

	Recomme	nded Action	
Non-heme toxicity	Lenalidomide	Carfilzomib	Elotuzumab
			restarted at the treating physician's discretion
CrCl>60 mL/min	Full dose	Full dose	Full dose
CrCl <60 mL/min > 30 mL/min	Reduce lenalidomide to 10 mg every 24 h; may reinstate prior dose if, after 2 cycles, CrCl normalizes	Full dose	Full dose

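### When a hold reaches the end of a cycle or Day 1 is delayed, Section 6.5 calls for one dose decrement, while some rows of Tables 6-5 and 6-6 call for no reduction, and nothing says which governs

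*Combined protocol and SAP*

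**What the plan says.** Section 6.5 sets the conditions for opening a cycle: ANC above 1.0 x 10^9/L, platelets at least 30 x 10^9/L, and other drug-related events back to grade 1 or baseline, with a further uric acid and creatinine condition in cycles 1 and 2. It then gives a dose rule with two triggers: "If elotuzumab, carfilzomib or lenalidomide are held for the remainder of the previous cycle or the new cycle is delayed due to residual toxicity". The consequence is that "then the new cycle will be started at 1 dose decrement". The sentence does not say whether the decrement falls on the held drug, on all three named drugs, or only on those with a lower level.

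Section 6.6 gives event-specific instructions:

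- Table 6-5, platelets below 30, carfilzomib: "With resolution restart at previous dose". The exception is a subsequent fall with bleeding or platelets below 10, which restarts one level lower.
- Table 6-5, first ANC below 0.75, lenalidomide: "Resume at full dose when ANC" reaches 0.75.
- Table 6-6, rash and arrhythmia rows, carfilzomib: hold until grade 1 or lower, then "reinstitute at current dose".
- Table 6-6, tumor lysis and herpes rows, both drugs: "Reinstitute at full doses". The grade 3 or 4 infection row also returns both drugs at full dose if there is no neutropenia.
- Item 6-4, elotuzumab: "No dose reductions for elotuzumab are allowed".

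**The concern.** A site that meets one of these events at the turn of a cycle finds two dosing instructions, both written in the protocol, and no order of precedence. The primary endpoint is read at the end of cycle 8, so dosing in cycles 2 to 8 is the exposure behind it. The safety and tolerability objective rests on the same exposure. Section 4.2.2 plans five centers. If they follow different passages, dose intensity will vary by center for reasons unrelated to the subject. An individual subject may return at an unreduced dose where 6.5 calls for a reduction, or be reduced where the table calls for none.

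**Working it through.** **The plan's own design figure.** Inputs from Section 10.2.1: n = 40, reject at 17 or more responses, null rate 30%, alternative 50%, one-sided alpha 0.10. With X binomial(40, p):

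- Type I error = P(X >= 17 | p = 0.30) = 0.063. A cut-off of 16 would give 0.115, so 17 is correct.
- Power = P(X >= 17 | p = 0.50) = 0.866, matching the stated figure of a little over 85%.

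No dosing rule enters this calculation, so the conflict leaves it unchanged.

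**Row-by-row comparison**, for events that last to the end of a cycle or delay Day 1. Section 6.5 gives one decrement in every case. Counts are x 10^9/L.

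| Event | Drug | Instruction in Section 6.6 | Against 6.5 |
|---|---|---|---|
| Platelets < 30: first fall, or later fall at 10-30 without bleeding | Carfilzomib | Previous dose | Conflict |
| Platelets: later fall with bleeding, or < 10 | Carfilzomib | One decrement | Agrees |
| Platelets < 30 | Lenalidomide | One decrement (a further one at each later fall) | Agrees |
| First ANC < 0.75 | Lenalidomide | Full dose | Conflict |
| ANC < 0.5 | Carfilzomib | One decrement | Agrees |
| Rash, arrhythmia | Carfilzomib | Current dose | Conflict |
| Tumor lysis, herpes, grade 3-4 infection without neutropenia | Both | Full dose | Conflict |
| Any hold | Elotuzumab | No reduced level exists | Decrement cannot be applied |

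**Case A: hold reaching cycle end.** In cycles 1-8 the last carfilzomib dose is on Day 15, and Section 6.4.2 does not replace missed doses within a cycle. Suppose platelets are between 10 and 30 on Day 15, without bleeding, and the dose is held and not rescheduled. Carfilzomib is then held for the rest of that cycle. If counts recover by the next Day 1, Table 6-5 gives the previous dose (70 mg/m2) and Section 6.5 gives one level lower (56 mg/m2). Lenalidomide is reduced under either passage, so only carfilzomib is in dispute.

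**Case B: delayed Day 1.** A first ANC of 0.6 on Day 1 fails the 6.5 condition. The cycle waits for ANC above 1.0 and then starts at one decrement. Table 6-5 resumes lenalidomide at full dose and, at ANC 0.5-0.75, tells sites to "Continue at full dose" for carfilzomib. Lenalidomide is 25 mg or 15 mg depending on the passage followed. Whether carfilzomib also drops depends on which drugs the 6.5 sentence means, and it does not say.

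**Size of one level**, from the dose-adjustment tables in Section 6.6:

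- Carfilzomib: (70 - 56)/70 = 0.20.
- Lenalidomide: (25 - 15)/25 = 0.40.

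**The case against.** The best defense is that the passages are layered: 6.5 governs new cycles and the tables govern restarts within a cycle. Some text points that way. Several Table 6-6 lenalidomide rows apply only if the event resolves before Day 21 of the current cycle. But those rows restart at one decrement anyway. The no-reduction rows listed above carry no such limit, and no passage states the layering. The thyroid row shows that the tables do reach into the next cycle: it restarts lenalidomide there at one decrement and leaves carfilzomib unadjusted.

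A second defense is oversight. Section 6.6 sends dose modifications that differ from the protocol to the Lead Principal Investigator, and Section 13.7 has bi-weekly multi-site calls on safety and adherence. These may narrow differences between sites. They do not settle precedence, because here both doses are stated in the protocol and a site following either one has no departure to raise.

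Four stronger readings are tempting, and the documents do not support them:

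- *The tables contradict 6.5 throughout.* They do not. Several rows agree, and a hold that resolves within the cycle without delaying Day 1 does not trigger 6.5. Infection or herpes not judged drug-related would not fail the Day 1 drug-related-event condition, so it would conflict only if the hold reaches cycle end. Item 6-4 gives no restart dose; its wording is clear that elotuzumab is not reduced.
- *The ANC thresholds clash.* A stricter count to open a cycle than to hold a drug within one is not a contradiction. Nor does it follow that milder neutropenia loses more dose: a subject with a mid-cycle ANC of 0.6 also meets 6.5 if lenalidomide stays held to cycle end or ANC is not above 1.0 on the next Day 1.
- *A subject loses 20% of carfilzomib and 40% of lenalidomide up to cycle 8.* From cycle 3 that would be 6 x 3 x 70 = 1260 against 6 x 3 x 56 = 1008 mg/m2, and 6 x 21 x 25 = 3150 against 6 x 21 x 15 = 1890 mg. This extreme case needs every dose given, no re-escalation, and both drugs in dispute at once. Some carfilzomib rows allow re-escalation, for example neuropathy and heart failure, and the documents give no frequency for any of these events.
- *The trial loses power.* Power would be 0.726 if the true rate were 46%, but nothing in the documents links a dose decrement to a fall of that or any size.

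**Conclusion.** The conflict is real but bounded. It arises only when a hold lasts to the end of a cycle or Day 1 is delayed for residual toxicity, and only for the rows marked as conflicts. In those cases the same event has two protocol-stated doses one level apart: 20% for carfilzomib and 40% for lenalidomide, measured from the nominal doses of 70 mg/m2 and 25 mg. For elotuzumab, 6.5 lists a drug to which its rule cannot be applied.

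This is a weakness in conduct and interpretation: exposure before the cycle-8 endpoint and the tolerability data can differ by site. It is not an error in the sample size, the alpha or the rejection rule. Its effect on the response rate cannot be calculated from the documents.

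**What to change.** Amend the protocol so that Section 6.5, item 6-4 and Tables 6-5 and 6-6 can be read together:

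1. State which passage governs when a hold reaches the end of a cycle or Day 1 is delayed.
2. State to which drug or drugs the 6.5 decrement applies.
3. Reconcile the mention of elotuzumab in that sentence with item 6-4.

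The sponsor's clinicians choose the rule; this review takes no position on which dose is right. The cost is a wording amendment and a memo to sites, with no added subjects or procedures.

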6.6. Dose-Modification Guidelines

The following sections and tables summarize dosing modifications of elotuzumab, carfilzomib, lenalidomide, and dexamethasone to manage possible toxicity. Dose modifications different from those stated in the protocol should be discussed with the Lead Principal Investigator. Administration of carfilzomib and lenalidomide will be discontinued in the event of any other toxicity that, in the opinion of the Lead, Secondary Site, or Treating Investigator, warrants discontinuation.

In addition to dose reductions, administration of elotuzumab, carfilzomib and lenalidomide will be held temporarily in the event of a treatment-related toxicity at the Treating Investigator's discretion. Study treatment may be reintroduced if resolution of the event to the baseline value or to \leq Grade 1 within 21 days; otherwise study drug will be permanently discontinued. Any deviations from this plan must be approved by the Lead Principal Investigator.

If a subject's elotuzumab administration is delayed on day 1 of a cycle, carfilzomib, lenalidomide, and dexamethasone will also be delayed until the elotuzumab is resumed, which would then become the new day 1 of that cycle.

If a subject's elotuzumab is held in the middle of a cycle, carfilzomib, dexamethasone, and lenalidomide dosing will continue as scheduled. If the subject's elotuzumab is delayed during the cycle and is resumed within the designated window, (+/-3 days Cycles 1 and 2; +/-7 days Cycles 3 and beyond) the subject may receive the scheduled dose. If the elotuzumab is not resumed within the given window (+/-3 days Cycles 1 and 2; +/-7 days Cycles 3 and beyond), the subject is to omit that dose, and resume dosing at the next dosing time point.

If a study drug (except dexamethasone) is discontinued, the subject may continue on trial. However, if the discontinuation happens prior to the end of cycle 8 (1^{ary} endpoint), the subjects will Page 45

continue to be treated and will only be included on the intent to treat analysis.

All clinically-significant non-hematologic toxicities must be resolved to Grade 1 or baseline.

Dose reduction levels of elotuzumab, carfilzomib, lenalidomide, and dexamethasone for toxicity management of individual subjects are provided below:

Table 6-1 Carfilzomib Dose Adjustments

Nominal carfilzomib dose	Dose -1	Dose -2	Dose -3	Dose -4
70 mg/m^2	56 mg/m^2	45 mg/m^2	36 mg/m^2	27 mg/m^2

Table 6-1 Lenalidomide Dose Adjustments

Nominal Lenalidomide Dose	Dose -1	Dose -2	Dose -3
25 mg Days 1-21	15 mg	10 mg	5 mg

Table 6-3 Dexamethasone Dose Adjustments

Nominal Dexamethasone Dose	Dose -1	Dose -2	Dose -3
40mg or 20 mg	Reduce dexamethasone by 50% from starting dose; however, the 20-mg IV dose of dexamethasone given before the infusion on the day of elotuzumab infusions must not be decreased.	dexamethasone on the day when elotuzumab is	Discontinue dexamethasone

^{*}Split dosing of dexamethasone on days 1,2, 8,9, 15,16, 22,23 may be implemented to control toxicities that do not require a dose reduction. Split dosing requires the approval of the Lead Principal Investigator

6-4 Elotuzumab Dose Adjustments

No dose reductions for elotuzumab are allowed. If Elotuzumab is held on Day 1 of a new cycle, treatment with carfilzomib/lenalidomide/dexamethasone will also be delayed. If elotuzumab is held during any cycle on days 8, 15, or 22, the treating investigator will decide if lenalidomide, carfilzominb, and/or dexamethasone will be held using recommended guidance for retreatment below. Treatment may be delayed for a maximum of 21 days (see section 6.5.2.1 for details).

6.6.1. Toxicity Management Guidelines

Treatment guidelines for specific hematologic toxicities are outlined in Section 7.5.1.1 and nonhematologic toxicities in Section 7.5.1.2. In addition to dose reductions, administration of carfilzomib and/or lenalidomide may be held temporarily in the event of a treatment-related toxicity at the Treating Investigator's discretion.

6.6.1.1. Hematologic Toxicity

Table 6-5 Dose Modification Guidelines for Hematologic Toxicities

When Platelets:	Lenalidomide	Carfilzomib		Elotuzumab
Fall to < 30 x 10 ⁹ /L	 Hold dose, follow CBC weekly Hold prophylactic anticoagulation until platelets return to ≥ 30 × 10⁹/L Then resume at 1 dose decrement 	If platelets 10-30 x10 ⁹ /L without evidence of bleeding	Hold With resolution restart at previous dose	Hold Upon resolution elotuzumab can be restarted at the treating physician's discretion
		If evidence of bleeding or platelets < 10 x10 ⁹ /L	Hold With resolution restart at previous dose	Hold Upon resolution elotuzumab can be restarted at the treating physician's discretion
For each subsequent drop to < 30 x $10^9/L$	 Hold dose, follow CBC weekly Hold prophylactic anticoagulation until platelets return to ≥ 30 × 10⁹/L Then resume at additional dose decrement 	If platelets 10-30 x 10 ⁹ /L without evidence of bleeding	Hold With resolution restart at previous dose	Hold Upon resolution elotuzumab can be restarted at the treating physician's discretion
		If evidence of bleeding or platelets < 10 x10 ⁹ /L	Hold With resolution restart at 1 dose decrement	Hold Upon resolution elotuzumab can be restarted at the treating physician's discretion

Grade 4 thrombocytopenia without evidence of bleeding, carfilzomib dosing may occur at the discretion of the Treating Investigator. However, subjects should receive supportive measures in accordance with institutional guidelines.

Table 6-5 Dose Modification Guidelines for Hematologic Toxicities

When ANC:	Lenalidomide	Carfilzomib		Elotuzumab
Fall to < 0.75 x 10 ⁹ /L	 Hold dose, administer myeloid growth factor Follow CBC weekly Resume at full dose when ANC ≥ 0.75 x 10⁹/L 	If ANC 0.5-0.75 x 10 ⁹ /L	Continue at full dose	Continue at full dose
		If ANC $< 0.5 \times 10^9 / L$	• Hold • Resume at 1 dose decrement when ANC returns to ≥ 0.5 x10 ⁹ /L	Hold Upon resolution elotuzumab can be restarted at the treating physician's discretion
For each subsequent drop to < 0.75 x 10 ⁹ /L	 Hold dose, administer myeloid growth factor Follow CBC weekly Resume at 1 dose decrement when ANC ≥ 0.75 x 10⁹/L 	If ANC 0.5-0.75 x 10 ⁹ /L	Continue at full dose	Hold Upon resolution elotuzumab can be restarted at the treating physician's discretion
		If ANC $< 0.5 \times 10^9 / L$	• Hold • Resume at 1 dose decrement when ANC returns to ≥ 0.5 x10 ⁹ /L	Hold Upon resolution elotuzumab can be restarted at the treating physician's discretion

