CrCl< 30 mL/min	Reduce lenalidomide to 15 mg every 48 h	Hold carfilzomib until CrCl> 30 mL/min. If attributed to carfilzomib, restart at 1 dose decrement. If tolerated, the reduced dose may be escalated to the previous dose at the discretion of the physician. If not attributed to carfilzomib, restart at dose used prior to the event. Frequent monitoring of renal function should then be implemented	Full Dose
CrCl< 30 mL/min requiring dialysis	5 mg once daily. On dialysis days the dose should be administered following dialysis.	Hold until resolved to ≤ Grade 2. Then restart carfilzomib at 1 dose decrement	Full Dose

Table 6-6 Dose Modifications for Non-hematologic Toxicity

	Recomme	nded Action	
Non-heme toxicity	Lenalidomide	Carfilzomib	Elotuzumab
Venous thrombosis/embolism ≥ Grade 3	Hold lenalidomide dose and adjust anticoagulation regimen; re-start at Treating Investigator's discretion at full dose	No adjustment required	No adjustment required
Hyperthyroidism or hypothyroidism	Omit lenalidomide for remainder of cycle, evaluate, and initiate appropriate therapy. Restart lenalidomide next cycle at 1 dose decrement	No adjustment required	No adjustment required
Congestive heart failure (CHF)	Any subject with symptoms of CHF, whether or not lenalidomide related, must have the dose held until resolution or return to baseline. If CHF was felt to be lenalidomide related, reinstate by one dose decrement after return to baseline. If no resolution of CHF after 2 weeks, the subject will be withdrawn from the study.	Any subject with symptoms of CHF, whether or not carfilzomib related, must have the dose held until resolution or return to baseline. If CHF was felt to be carfilzomib related, reinstate by one dose decrement after return to baseline. If tolerated, the reduced dose may be escalated to the previous dose at the discretion of the physician. If no resolution of CHF after 2 weeks, the subject will be withdrawn from the study.	Hold Upon resolution elotuzumab can be restarted at the treating physician's discretion
Hypertension including Hypertensive Crises	NA	≥ Grade 3: Carfilzomib attribution, hold drug until resolved to ≤ Grade 2. Resume at one level dose reduction	NA

Table 6-6 Dose Modifications for Non-hematologic Toxicity

	Recomm	ended Action	
Non-heme toxicity	Lenalidomide	Carfilzomib	Elotuzumab

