- 2. Includes baseline symptoms, neuropathy history and documentation of the CTCAE grade if peripheral neuropathy is present at baseline.
- 3. May be within 3 months of planned start. Includes: lateral radiograph of skull, anteroposterior and lateral views of the spine, and anteroposterior views of the pelvis, ribs, femora, and humeri. Skeletal surveys performed outside of the 30-day window may be considered for inclusion after discussion with the Lead Principal Investigator. Skeletal survey only needs to be repeated throughout the trial if clinically indicated.
- 4. 12-Lead ECG including QTc interval. ECG should be performed throughout the study only as clinically indicated
- 5. Echocardiogram must be completed at screening to demonstrate LVEF ≥ 50%. ECHO may be performed throughout the study if clinically indicated.

- 6. For Day 1 of cycle 1, screening results may be used if within 7 days of treatment start. Complete physical exam (including vital signs, [systolic and diastolic blood pressure, respiration, pulse, oral temperature], height, weight, calculation of body surface area [BSA]) and ECOG score required at screening at Day 1 of each cycle (height only required at screening). Symptom-directed Physical Exam on Days 8, 15, (and 22 on cycles 1-2)
- 7. Systolic and diastolic blood pressure, pulse, respiration, temperature before and after elotuzumab infusion and approximately 1 hour before carfilzomib dosing on days where only carfilzomib is dosed.
- 8. Hemoglobin, WBC with complete differential, RBCs, platelet count, absolute neutrophil and lymphocyte counts. Results must be reviewed before dosing. On cycles 1-8, these tests will be required on days 1, 8, and 15 prior to infusion and on cycles 9+ they will be required on days 1 and 15 prior to infusion.
- 9. Full serum chemistry panel at screening, days 1, 8, and 15, and EoT for all subjects: sodium, potassium, chloride, creatinine, glucose, uric acid, phosphorus, magnesium, LDH, total bilirubin, C-Reactive Protein. Results must be reviewed before dosing. On cycles 1-8, these tests will be required on days 1, 8, and 15 prior to infusion and on cycles 9+ they will be required on days 1 and 15 prior to infusion.

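### For within-cycle carfilzomib doses, the note under Table 6-5 allows dosing in non-bleeding Grade 4 thrombocytopenia with no platelet floor, against the row that holds below 10 × 10⁹/L; a smaller mismatch in Table 6-6 concerns attributed lung clots

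*Combined protocol and SAP*

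**What the plan says.** **Platelets.** Table 6-5 (section 6.6.1.1) has four carfilzomib cells for counts below 30 × 10⁹/L: two count bands, each at the first drop and at later drops. All four hold the drug. For 10–30 without bleeding, the cell reads "Hold With resolution restart at previous dose" at either drop. The other band is introduced by "If evidence of bleeding or platelets < 10" (× 10⁹/L). Because of the *or*, a count below 10 is a hold even when the subject is not bleeding. The restart is at the previous dose after the first drop and one decrement lower after later drops.

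The note under these rows says: "Grade 4 thrombocytopenia without evidence of bleeding, carfilzomib dosing may occur at the discretion of the Treating Investigator". Its next sentence asks for supportive measures under institutional guidelines. It names no lowest count and does not say how it relates to the rows.

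Section 6.5 requires at least 30 × 10⁹/L on Day 1 of a new cycle; otherwise "a new treatment cycle will not be initiated until the toxicity has resolved, as described above". Appendix 6, note 8, requires blood counts before every scheduled weekly carfilzomib infusion: "Results must be reviewed before dosing".

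**Lung clot.** In Table 6-6 (section 6.6.1.2), the carfilzomib cell of the row "Venous thrombosis/embolism ≥ Grade 3" is "No adjustment required". A separate row covers clot, fluid or bleeding in the lungs. For a Grade 3 or higher event attributed to carfilzomib, it holds the drug until Grade 1 or lower and then resumes one dose level down.

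**The concern.** These are safety instructions for a four-drug regimen given at five centers, and section 1.6 presents required dose modifications as part of making safety the first priority. Two sites could read Table 6-5 correctly and act in opposite ways on the same subject. With a non-bleeding count below 10 × 10⁹/L on Day 8 or 15, one would hold carfilzomib and the other could give it. The count will be known before the dose, so the wording decides what happens.

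The lung-clot rows raise the same kind of question in a narrower setting. The thrombosis row excludes neither lung events nor carfilzomib-attributed events, and no text says which row takes precedence.

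**Working it through.** No sample-size, power or error-rate figure is involved. The check sets the instructions side by side.

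**1. Platelets, subject not bleeding, carfilzomib action (Table 6-5)**

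| Count (× 10⁹/L) | First drop | Later drop | Note |
|---|---|---|---|
| 10–30 | Hold; restart at previous dose | Hold; restart at previous dose | May dose, if Grade 4 |
| Below 10 | Hold; restart at previous dose | Hold; restart one decrement lower | May dose |

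**2. Does the unprinted Grade 4 cut-off matter?** Appendix 3 gives only the grading version and a link. Call the cut-off *c* and vary it from 10 to 50 × 10⁹/L, so that counts below 10 are always Grade 4.
- *c* from 10 to 30: every non-bleeding Grade 4 count lies in a hold row.
- *c* above 30 and up to 50: the part below 30 still does.
- If *c* is below 30 and the note overrides the rows, counts from *c* to 30 must be held while lower counts may be dosed.

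The below-10 conflict is present throughout the range.

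**3. Does other text settle it?**
- Section 6.5 does so for Day 1 of a new cycle only. On the weekly schedule, that leaves Days 8 and 15 in cycles 1–8 and Day 15 from cycle 9.
- The elotuzumab paragraph of section 6.6 covers holds on Days 8, 15 and 22: "the treating investigator will decide if lenalidomide, carfilzominb, and/or dexamethasone will be held using recommended guidance for retreatment below". For platelets, that guidance is Table 6-5 itself, so the route is circular.
- Section 6.6 asks for discussion with the Lead Principal Investigator when a modification departs from the protocol. Holding and dosing are both in the protocol, so neither clearly triggers this.

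**4. Lung clot, Grade 3 or higher, attributed to carfilzomib (Table 6-6)**
- Thrombosis row: no carfilzomib change. Lung row: hold, then one level down. From full dose, Table 6-1 gives 70 to 56 mg/m², and 56/70 = 0.80, a 20% reduction per dose.
- Section 6.5: no new cycle until a drug-related event is back to Grade 1 or baseline, and a cycle delayed for residual toxicity starts one decrement lower.
- Section 6.6: clinically significant non-hematologic toxicity must resolve to Grade 1 or baseline, without stating whether this governs doses inside a cycle.

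With these rules applied, two differences remain: whether remaining doses in the same cycle are given, and whether the dose is reduced when the event resolves before the next Day 1.

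**The case against.** **The note is a deliberate exception.** This is the natural reading. The note sits directly under the platelet rows, concerns carfilzomib only, is permissive, excludes bleeding and asks for supportive measures; section 6.3.4 allows platelet transfusion. A default hold followed by a discretionary exception is ordinary drafting. That answers the charge of flat contradiction for counts of 10 and above. It does not answer the case below 10: there the table holds non-bleeding subjects expressly, and an exception without a floor removes that hold. Whether discretion should stop at 10 is partly a clinical judgment, but the protocol should not state both rules.

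**The lung row is the more specific one.** It is narrower in both site and attribution, so treating it as governing is plausible. The thrombosis row sets no mandatory change but does not forbid a hold, and sections 6.6 and 6.6.1 let the investigator hold carfilzomib for treatment-related toxicity. This objection largely stands and is why the lung-clot part is secondary. What survives is that no text gives the precedence.

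**Stronger readings to avoid.** A reader might infer that the thrombosis row lets a subject continue indefinitely at 70 mg/m² after an attributed lung clot. The resolution rules in sections 6.5 and 6.6 do not support that. A reader might also take the share of scheduled carfilzomib doses falling after Day 1 as the size of the problem. That share counts every such dose whatever the platelet count, so it shows where the wording could apply, not how often it would.

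**Conclusion.** The platelet point holds for within-cycle carfilzomib doses. Table 6-5 requires a hold below 10 × 10⁹/L without bleeding, the note permits dosing there, and nothing else in the protocol resolves the two. The only outside assumption is that counts below 10 × 10⁹/L are Grade 4. Doses on Day 1 of a new cycle are not affected.

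The lung-clot point holds in a limited form: two rows give different carfilzomib actions for the same attributed event. The practical difference is confined to the rest of that cycle and to a possible one-level reduction when the event clears before the next Day 1. Clots not attributed to carfilzomib do not raise this carfilzomib conflict.

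The documents give no frequency for non-bleeding Grade 4 thrombocytopenia or for attributed lung clot, so no expected number of affected doses can be stated. The primary endpoint test, its alpha and its power do not change. This is a safety-wording matter that should be fixed.

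**What to change.** Reword the note under the platelet rows, for example: *As an exception to the Hold row, and for within-cycle doses only, the Treating Investigator may give carfilzomib, with supportive measures, in Grade 4 thrombocytopenia when platelets are at least 10 × 10⁹/L and there is no bleeding. Below 10 × 10⁹/L, or with bleeding, always hold.*

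Keep the Grade 4 condition. Granting discretion for all counts from 10 to below 30 would, if the Grade 4 cut-off is under 30, allow dosing where the present text requires a hold. Keeping it means that, with such a cut-off, counts between the cut-off and 30 stay on hold while somewhat lower ones may be dosed. That ordering already follows from the exception reading, and whether to change it is a clinical decision for the sponsor.

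In the carfilzomib cell of the venous thrombosis/embolism row, add: *except a Grade 3 or higher lung clot attributed to carfilzomib, for which the lung row applies.*

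The cost is a wording amendment, with no change to sample size, visits or data collection. Investigators lose discretion below 10 × 10⁹/L, and a few more carfilzomib doses may be held.
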